## 6.2 Study Visits

Prior to the signing of informed consent and assent (as applicable), the investigator or designee will explain the purpose of the study, procedures, and subject responsibilities to the potential study subject and/or caregiver (as applicable). The subject's and/or caregiver's willingness and ability to meet the follow-up requirements of the study will be determined.

The schedule of visits is presented in [Table 1](#). Details about study procedures and how they are to be performed are presented in [Section 7](#).

### 6.2.1 Screening / Baseline

Screening procedures will occur prior to randomization and will include:

- Informed consent and assent (as applicable)
- Medical history
- Prior and concomitant medications
- Physical examination
- Urine pregnancy test (in female subjects of childbearing potential only)
- Otomycosis signs and symptoms
- Determination of subject eligibility for the study

Subjects who are eligible for the study will undergo the following additional procedures:

- Subject global assessment
- Microbial culture (fungi and bacteria)
- Ear cleaning
- Randomization
- Weighing of study drug, followed by dispensation of study drug to subject
- Dispensation of subject diary to subject.
- Administration of the first dose by the subject or caregiver under the supervision of the investigator or other study personnel
- Collection of AE information, with the time of AEs to be reported as occurring either before or after the first dose of study drug
- Subject instruction about the date on which they are to stop administering study drug (after all doses have been administered on Day 7 for the 7-day group, and after all doses have been administered on Day 14 for the 14-day groups; subjects will be instructed that study drug should be stopped on the appropriate date regardless of the date for which the next visit is scheduled)

- Subjects will be instructed to bring their bottle of study drug and the diary to the site for their next visit

### **6.2.2 On Treatment**

These visits may occur up to 3 days later than the specified day. Subjects randomized to the 7-day group will not have any On Treatment visits and will instead proceed directly to the procedures specified for the End of Treatment Visit. Subjects randomized to the 14-day groups will have one On Treatment visit on Day 8.

Subjects will be instructed not to administer any study drug on the day of this visit until after the visit has occurred, if the visit is scheduled for the morning. If the visit is scheduled for the afternoon, subjects will be instructed that the morning dose of the study drug can be administered prior to the visit.

The following procedures and evaluations will occur during the On Treatment visits:

- Otomycosis signs and symptoms
- Subject global assessment
- Ear cleaning
- AE evaluation
- Review of concomitant medications
- Weighing of study drug and return of the bottle of study drug to the subject
- Review of subject diary.
- Subject reminder to continue to administer their assigned study drug twice daily up through the date on which they are to stop administering study drug (after all doses have been administered on Day 14; study drug should be stopped on the appropriate date regardless of the date for which the next visit is scheduled)
- Subjects will be instructed to bring their bottle of study drug and the diary to the site for their next visit

### **6.3 End of Treatment**

This visit may occur up to 3 days later than the specified day. Subjects randomized to the 7-day group will have the End of Treatment Visit on Day 8, and subjects randomized to the 14-day groups will have the End of Treatment Visit on Day 15.

The following procedures and evaluations will occur during the End of Treatment visits:

- Otomycosis signs and symptoms
- Subject global assessment
- Microbial (fungal) culture
- Ear cleaning (in subjects randomized to the 7-day group only)
- AE evaluation
- Review of concomitant medications
- Collection of subject diary
- Collection/weighing of study drug

### **6.4 Test of Cure**

This visit may occur up to 1 day sooner or up to 8 days later than the specified day. Subjects randomized to the 7-day group will have the Test of Cure Visit on Day 15, and subjects randomized to the 14-day groups will have the Test of Cure Visit on Day 22.

The following procedures and evaluations will occur during the Test of Cure Visit:

- Otomycosis signs and symptoms
- Subject global assessment
- Microbial (fungal) culture
- AE evaluation
- Review of concomitant medications
- Urine pregnancy test (in female subjects of childbearing potential only)

In case of early termination, the procedures planned for the Test of Cure Visit should be performed if possible.

## **6.5 Unscheduled Study Visits**

Additional visits may be scheduled, as necessary, to ensure the safety and well-being of subjects. All additional examinations should be fully documented in the source files and eCRFs, as appropriate. Visits that fall outside the designated scheduled visit window but that are intended to fulfill scheduled visit requirements will be collected and transcribed to the appropriate scheduled visit eCRF.

If a subject is seen for multiple visits during a given visit time frame, the data from the visit(s) that are intended to meet the protocol requirements for the scheduled visit should be captured on the visit eCRF. Any other data from any additional visits within a scheduled visit interval will be captured elsewhere on the eCRF.

## **6.6 Post-study Follow-up**

If a subject requires further follow-up of AEs upon discontinuation or completion of the study, the investigator should schedule post-study follow-up visits, as necessary.

## **6.7 Missed Visits**

If a subject misses any scheduled follow-up visit and cannot be seen prior to the start of the visit range for the next scheduled follow-up visit, the visit is considered missed.

## **6.8 Subject Completion**

The subject has completed the study when the Test of Cure Visit is completed. Subjects who require further follow-up for an AE will be followed according to Section 6.6.

## **6.9 Early Study Termination**

The sponsor reserves the right to terminate this study prematurely. If during the study it becomes evident to the sponsor that the study should be stopped prematurely, the study will be terminated and appropriate notification will be given to the investigator, IRB, and FDA, as applicable. The sponsor or designee will instruct the investigator to stop randomizing subjects and to arrange for study closeout at the site.

## 7 STUDY PROCEDURES

The required study procedures are detailed in this section. The timeline for these procedures is presented in [Section 6](#).

### 7.1 Medical/Medication History

At Screening/Baseline, the investigator or designee will interview each subject and obtain a complete medical and medication history, including a history of all surgeries and past medical procedures. The subject must not require any treatment or medication for concurrent illnesses as specified by the inclusion and exclusion criteria or anticipate the need for any excluded concomitant medications.

### 7.2 Physical Examination

At Screening/Baseline, the investigator or designee will perform a complete physical examination to include the following: general appearance; head, eyes, ears, nose, throat; neck; cardiovascular; lungs; abdomen; lymph nodes; extremities; neurological; skin; and musculoskeletal.

### 7.3 Urine Pregnancy Test

The urine pregnancy test (performed in females of childbearing potential only) must have a minimum sensitivity of 25 mIU of  $\beta$ -hCG/mL of urine.

### 7.4 Otomycosis Signs and Symptoms

The signs and symptoms of otomycosis will be assessed according to the scales for pruritus (see [Section 7.4.1](#)), debris (see [Section 7.4.2](#)), presence of fungal elements (see [Section 7.4.3](#)), and pain (see [Section 7.4.4](#)). The same evaluator should assess each subject for signs and symptoms of otomycosis at each visit throughout the subject's participation in the study, if possible.

#### 7.4.1 Pruritus

##### 7.4.1.1 Subject Assessment

Subjects or their caregivers (as appropriate, based on the age of the subject) will be handed a questionnaire for each ear being treated with study drug and asked to indicate the choice that most closely reflects the severity of itching in the ear over the last 24 hours. Choices and scores will be according to the following scale:

| Score | Category | Description   |
|-------|----------|---|
| 0     | None     | No itching  |
| 1     | Mild     | Occasional itch, not interfering with daily activities                |
| 2     | Moderate | Fairly persistent itch, partially tolerated; sleep is not interrupted |
| 3     | Severe   | Intolerable, constant itch; sleep is interrupted                      |

#### 7.4.1.2 Investigator Assessment

After subjects have completed the questionnaire described in [Section 7.4.1.1](#), subjects or their caregivers (as appropriate, based on the age of the subject) will be asked by the investigator (or designee) about the severity of itching present in each ear being treated with study drug. Questions such as the following will be used in order to gather information for this assessment:

“Have you had itching in your ear over the last day or so?”

“Over the last 24 hours, has your itching interfered with your daily activities?”

“Over the last 24 hours, has your itching been bad enough to keep you awake?”

“Over the last 24 hours, would you describe your itching as intolerable or constant?”

The investigator will then score the symptom of pruritus for each ear being treated with study drug, taking into consideration the subject’s and/or caregiver’s answers and the investigator’s observations of the subject. Scores will be according to the same scale as described in [Section 7.4.1.1](#).

#### 7.4.2 Debris

Upon otoscopic examination, the investigator will score the amount of debris present in each ear being treated with study drug. Scores will be according to the following scale:

| Score | Category | Description  |
|-------|----------|--|
| 0     | None     | No debris present  |
| 1     | Scant    | Debris minimally present, but with no notable occlusion of external ear canal                    |
| 2     | Moderate | Debris present with partial occlusion of external ear canal; tympanic membrane can be visualized |
| 3     | Heavy    | Complete occlusion of ear canal; tympanic membrane cannot be visualized                          |

### 7.4.3 Presence of Fungal Elements

Upon otoscopic examination, the investigator will assess the presence of fungal elements in each ear being treated with study drug. Scores will be according to the following scale:

| Score | Category | Description  |
|--------------|-----------------|---|
| 0            | Absent          | No fungal elements present on visual inspection with otoscope   |
| 1            | Present         | Fungal elements present on visual inspection with otoscope, such as visualization of white filaments in debris; black, gray, bluish, yellow, or white discharge; white debris with hyphae; or moist white plugs with black debris; or other observations that in the investigator's judgment are indicative of the presence of fungus |

### 7.4.4 Pain

Subjects or their caregivers (as appropriate, based on the age of the subject) will be asked by the investigator (or designee) whether pain is present in each ear being treated with study drug. Questions such as the following will be used in order to gather information for this assessment:

“Over the last 24 hours, has your ear hurt?”

“Over the last 24 hours, has your pain been constant?”

“Over the last 24 hours, would you characterize your pain as more dull or sharp?”

“Over the last 24 hours, have you had pain when your earlobe or the front part of your ear is touched?”

“Over the last 24 hours, have you felt pain inside your ear?”

“Over the last 24 hours, have you felt pain on the outside of your ear?”

The investigator will then score the symptom of pain for each ear being treated with study drug, taking into consideration the subject's and/or caregiver's answers and the investigator's observations of the subject. Scores will be according to the following scale:

| Score | Category | Description                            |
|--------------|-----------------|---|
| 0            | Absent          | No pain                                       |
| 1            | Present         | Pain present, easily tolerated to intolerable |

## 7.5 Subject Global Assessment

Subjects or their caregivers (as appropriate, based on the age of the subject) will be asked to choose among the following three options to assess the overall level of discomfort in each ear being treated with study drug. Subjects or their caregivers will be handed a questionnaire for each ear being treated with study drug and asked to indicate the choice that most closely reflects the subject's situation with the ear. Choices and scores will be according to the following scale:

| Score | Category | Description   |
|-------|----------|---|
| 0     | None     | My ear is not causing me any discomfort and is not stopping me from my normal activities                |
| 1     | Minor    | My ear is slightly uncomfortable, but it is not for the most part stopping me from my normal activities |
| 2     | Moderate | My ear is uncomfortable, and it is stopping me from at least some of my normal activities               |

## 7.6 Microbial Culture

At designated visits, the investigator or designee will obtain a sample from the external ear to be sent to a laboratory for microbial culture (for both fungi and bacteria at the Screening/Baseline visit and for fungi only at the End of Treatment and Test of Cure visits). Techniques for obtaining and handling the sample and sending it to the laboratory will be described in a separate laboratory manual. If both ears will be treated with study drug, both ears will be cultured.

## 7.7 Ear Cleaning

At designated visits, the investigator or designee will clean the ear(s) that are being/have been treated with study drug, according to the site's normal procedures. Ear(s) being treated will be cleaned at the designated visits even if they appear clear of debris. In cases in which the investigator would normally not clean the ear because it appears to be clear, this cleaning may be minimal. All ear cleaning will be documented in the eCRF.

## 7.8 Adverse Event Evaluations

See [Section 8](#).

## 7.9 Randomization

See [Section 9.2](#).

## 7.10 Study Drug Administration

See [Section 9.1.1](#).

## **7.11 Treatment Compliance**

Subjects or their caregivers (as appropriate) will complete a diary documenting each study drug administration. Additionally, each bottle of study drug will be weighed by the investigator or designee before dispensation to the subject and at each visit in which the used bottle is brought to the site.

## **7.12 Protocol Deviations**

The IRB-approved protocol must be followed except in the case of a change that is intended to eliminate an immediate risk to subjects.

The date of, nature of, and reason for deviations will be documented and explained by the investigator in all cases. Significant or major protocol deviations impacting the safety of the subject or the integrity of the study must be reported by the investigator to the sponsor and/or its designee and to the IRB immediately. Reporting of all other protocol deviations must adhere to the requirements of the governing IRB.

All changes to the protocol will be made by the sponsor or designee as an approved amendment to the protocol, submitted to the FDA, and approved by the IRB prior to implementation. New or altered consent forms required by the IRB due to a protocol revision must be signed by all subjects currently enrolled in the study and must be used for any subsequent subject enrollment.

## 8 ADVERSE EVENTS

### 8.1 Definition of an Adverse Event

An AE is any untoward medical occurrence in a subject or clinical investigation subject administered a study drug and which does not necessarily have a causal relationship with the study drug. An AE can therefore be any unfavorable and unintended sign (including a clinically significant abnormal laboratory finding), symptom, or disease temporally associated with the use of an investigational or marketed study drug, whether or not considered related to the investigational or marketed study drug. AEs include any illness, sign, or symptom that has appeared or worsened during the course of the clinical trial, regardless of causal relationship to the study drug. Study drug includes the investigational drug under evaluation and the comparator product.

Medical conditions/diseases present before signing the informed consent form are only considered AEs if they worsen after the informed consent form is signed.

AEs may be either spontaneously reported or elicited during questioning and examination of a subject. At each examination or visit, study personnel will ask each subject the following question, "Have you had any problems since we last spoke?" If known, the investigator should report the diagnosis of the underlying illness or disorder, rather than its individual symptoms.

#### 8.1.1 Definition of a Serious Adverse Event

An SAE is any untoward medical occurrence occurring at any dose that results in any of the following outcomes:

- Results in death
- Is life-threatening (defined as an event in which the subject was at risk of death at the time of the event; it does not refer to an event which hypothetically might have caused death if it were more severe)
- Requires inpatient hospitalization or prolongation of existing hospitalization
- Results in persistent or significant disability/incapacity
- Is a congenital anomaly/birth defect
- Is an important medical event (defined as a medical event(s) that may not be immediately life-threatening or result in death or hospitalization but, based upon appropriate medical and scientific judgment may jeopardize the patient/subject or may require medical or surgical intervention to prevent one of the other serious outcomes listed in the definition above). Examples of such events include, but are not limited to: allergic bronchospasm requiring intensive treatment in an emergency room or at home; blood dyscrasias or convulsions that do not result in inpatient hospitalization; the development of drug dependency or drug abuse.

Treatment on an outpatient emergency basis that does not result in hospital admission, or a hospitalization that is elective or is a preplanned treatment for a pre-existing condition that has not worsened since the start of the study, is not considered an SAE.

## **8.2 Severity of Adverse Events**

The severity of an AE will be determined by the investigator according to the following definitions:

- **Mild:** Awareness of event, but easily tolerated and does not disrupt usual activity
- **Moderate:** Discomfort sufficient to cause interference with usual activity
- **Severe:** Incapacitating, with inability to perform usual activities

## **8.3 Relationship of Adverse Events to Study Drug**

The relationship of AEs to the study drug will be assessed by the investigator according to the following definitions:

- **Not suspected:** The temporal relationship of the event to the study drug makes a causal relationship unlikely, or, other drugs, therapeutic interventions or underlying conditions provide a sufficient explanation for the observed event.
- **Suspected:** The temporal relationship of the event to the study drug makes a causal relationship possible or other drugs, therapeutic interventions or underlying conditions do not provide a sufficient explanation for the observed event.

If there is any valid reason, even if undetermined, for suspecting a possible cause-and-effect relationship between the study drug and the occurrence of the AE, then the AE should be considered “suspected.”

If the relationship between the AE and the study drug is determined by the sponsor to be “suspected,” the event will be considered to be related to the study drug for the purposes of expedited regulatory reporting.

## **8.4 Documentation of Adverse Events**

All AEs must be completely recorded on the Adverse Events section of the eCRF. The collection of AE information should begin after the subject has signed informed consent and continue up through the Test of Cure Visit. Subjects experiencing AEs that cause interruption or discontinuation of study drug, or those experiencing AEs that are present at the end of their participation in the study or that resulted in permanent discontinuation will receive follow-up as appropriate until the AEs have either resolved or have stabilized.

For each AE, the Investigator will evaluate and report the following:

- Onset (date);
- Resolution (date);
- Severity grade (mild, moderate, severe);

- Relationship to study drug (not suspected, suspected);
- Action taken (none, study drug temporarily interrupted, study drug permanently discontinued, concomitant medication taken, hospitalization/prolonged hospitalization, other);
- Serious (yes/no);
- Whether the AE occurred at the study drug application site (yes/no);
- For AEs of the ear, which ear (left, right, or both) was affected.

#### **8.4.1 Additional Reporting Requirements for Serious Adverse Events**

All SAEs that occur from the time the subject has signed the informed consent until the Test of Cure Visit will be reported. Additionally, any SAEs “suspected” to be related to the study drug and discovered by the investigator at any time after the study should be reported. Each of these SAEs must be reported to the sponsor’s designee within 24 hours of the occurrence of the SAE, or within 24 hours of learning of the SAE. Information on recurrent episodes, complications, or progression of the initial SAE must also be reported within 24 hours of the investigator receiving the information.

Reporting may be by telephone, confirmed facsimile transmission, or confirmed email to the medical monitor. The investigator must assess the relationship of the SAE to study drug and must complete the SAE form. If only limited information is initially available, follow-up reports are required. Follow-up information (e.g., discharge summary) will be retained in the subject’s chart and a copy (with the subject’s personal information removed and with the subject identified only by subject number) will be sent by confirmed facsimile transmission or confirmed email to the medical monitor. In the event of death, if an autopsy is performed, a copy of the report (with the subject’s personal information removed and with the subject identified only by subject number) should be sent to the medical monitor.

As required and after the sponsor’s review and determination of causality, the sponsor and/or designee will notify investigators of all AEs that are serious, unexpected, and considered by the investigator to have a suspected relationship to the study drug. This notification will be in the form of an update to the Investigator’s Brochure (i.e., “15-day letter”). An AE, whether serious or non-serious, is designated unexpected (unlabeled) if it is not reported in the clinical safety section of the Investigator’s Brochure or if the event is of greater frequency, specificity or severity.

Upon receiving such notices, the investigator must review and retain the notice with the Investigator’s Brochure and immediately submit a copy of this information to the responsible IRB according to local regulations. The investigator and IRB will determine if the informed consent requires revision. The investigator should also comply with the IRB procedures for reporting any other safety information. Follow-up reports should be submitted when requested or when pertinent information becomes available.

The sponsor will report all SAEs to the US FDA on the appropriate schedule depending on the event's expectedness and relationship to study drug based on the available information as presented in the Investigator's Brochure.

Any SAE occurring after the Test of Cure Visit and which is not considered to be of "suspected" relationship to study drug does not need to be reported.

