## **1.2 Compliance with Good Clinical Practice**

The investigator and all study staff will conduct the study in compliance with this protocol and FDA regulations, all applicable federal, state, and local laws, rules and regulations relating to the conduct of a clinical study, the ethical principles of the Declaration of Helsinki, and the current International Conference on Harmonisation (ICH) Good Clinical Practice (GCP) guidelines.

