### **3.2 Investigators**

The study will be conducted at up to 10 investigative sites located in the US.

The study will be conducted by investigators who are determined by the sponsor to be suitably qualified by training and experience to conduct this study in compliance with all applicable GCP and FDA federal regulations or local regulations. Sub-investigators will be identified on the Form FDA 1572.

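### Section 8.4.1 ties safety notices to the investigator's causality view alone, so the protocol does not require other sites to be told of a serious unexpected event that only the sponsor suspects

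*Protocol*

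**What the plan says.** Causality is first rated at the site. Protocol Section 8.3 states: "The relationship of AEs to the study drug will be assessed by the investigator according to the following definitions", with two categories, suspected and not suspected. The same section then adds a sponsor step. Where the sponsor's own determination is that a causal link is suspected, the stated consequence is that "the event will be considered to be related to the study drug for the purposes of expedited regulatory reporting".

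Section 8.4.1 covers notices to investigators. Its sentence opens by saying that the notice is given as required, and places it after the sponsor has reached its own view of causality. The criterion it then sets for an event to be notified is: "serious, unexpected, and considered by the investigator to have a suspected relationship to the study drug". The next paragraph sets out what follows once an investigator has received such a notice: it is kept on file, a copy goes to the responsible IRB, and the investigator and IRB decide whether the consent form needs revising.

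On the regulator, Section 8.4.1 says: "The sponsor will report all SAEs to the US FDA on the appropriate schedule", the timing depending on expectedness and relationship. Section 3.2 says: "The study will be conducted at up to 10 investigative sites located in the US".

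**The concern.** The two sections give causality to different people for two linked duties. For expedited reporting the sponsor's view counts. For telling investigators the stated criterion is the investigator's view, even though the sentence has just required the sponsor to form its own. The sponsor's determination is a step on the way to the notice and is not used to decide which events are notified.

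This matters when the two disagree. SAEs from all sites go to the sponsor's designee within 24 hours, so the sponsor can compare events across sites. A single investigator sees only local subjects and may reasonably rate an isolated event as not suspected. If the sponsor then takes a different view, that judgement is the new safety information, and the notice criterion leaves it out.

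**Working it through.** There is no figure to recompute. The check sets the two triggers side by side and then looks for any other route to the sites.

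**Inputs**
- Trigger for treatment as related in expedited reporting: the sponsor determines suspected (protocol 8.3).
- Trigger for notice to investigators: serious, unexpected, and suspected by the investigator (protocol 8.4.1).
- Trigger for IRB submission and consent review at a site: receipt of that notice (protocol 8.4.1, following paragraph).

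**The four causality combinations for a serious, unexpected event, read literally**

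| Sponsor | Investigator | Treated as related under the 8.3 sponsor sentence | Notice to investigators required by 8.4.1 |
|---|---|---|---|
| Suspected | Suspected | Yes | Yes |
| Suspected | Not suspected | Yes | No |
| Not suspected | Suspected | Sentence not engaged; 8.3 does not exclude it | Yes |
| Not suspected | Not suspected | No | No |

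The second row is the gap. The event is related for regulatory purposes, the notice is not required, and the IRB and consent steps that depend on the notice do not start at the other sites.

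**Is there another route?**
- The remaining text of 8.4.1 sends all SAEs to the FDA but names no further route to sites.
- Section 8.4.1 also asks investigators to follow IRB procedures for other safety information. That helps only where the investigator already has the information.
- Section 1.2 commits the investigator and study staff to "conduct the study in compliance with this protocol and FDA regulations", and Section 11.2 repeats this. Neither states a rule for sponsor notices.
- SAP Section 6.8.3 covers only the summary and listing of adverse events. SAP Section 6.1.6, despite a title that includes data monitoring, deals only with treatment allocation.

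No passage in either document requires the notice in the second row.

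**The case against.** The best defence is that the sentence is loosely drafted and the intent is sound. It says the notice is given as required, which points to outside obligations, and it puts the sponsor's causality determination first. That step would have little purpose if only the site's rating counted. Sections 1.2 and 11.2 add a general commitment to FDA regulations and GCP. Part of this stands: the text does not bar a wider notice, and a sponsor following its regulatory duties might well send one. But the words that select the events still name only the investigator, and staff working from the protocol would apply those words.

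Some stronger readings are tempting, and the documents do not support them.

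- **That the event would never reach the other sites.** The documents show only that the protocol does not require it to.
- **That there is an equal gap in the reverse case**, where the investigator suspects and the sponsor does not. Section 8.3 says what happens if the sponsor suspects; it does not say only if. All SAEs go to the FDA in any case, and the schedule rule does not name whose causality view governs. No unreported event is shown.
- **That the guinea-pig hearing loss makes a missed signal likely.** Section 1.3.1 reports hearing loss in all animals given vehicle or miconazole oil and none in the saline controls. It also attributes the loss to a large volume blocking conduction in a small animal, and reports no hearing loss in the clinical studies or post-marketing experience of a product with an almost identical vehicle. That does not exclude a risk, but it does not establish one in humans either.
- **That nine sites and nine IRBs would be left uninformed.** With all 10 sites open there would be 10 − 1 = 9 others, but the protocol says up to 10 and does not say whether sites have separate IRBs or share one.

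It is also fair to say that such events will be rare. That limits the priority of the point without removing the inconsistency.

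**Conclusion.** The point holds in a limited form. Sections 8.3 and 8.4.1 name different causality decision makers, and as written the protocol does not require other sites to be notified of a serious unexpected event that the sponsor suspects and the reporting investigator does not. The IRB submission and consent review that depend on the notice are then not triggered at those sites.

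The size cannot be put as a rate, because the documents give no expected frequency of SAEs or of disagreement on causality. With about 75 subjects and up to 30 days each, few such events should be expected. The point concerns subject safety and does not touch the efficacy analysis.

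The conclusion rests on three assumptions: the criterion is applied as written, more than one site is open, and no safety procedure outside these documents already sets a wider notice rule.

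**What to change.** In Section 8.4.1, extend the causality criterion for notices so that it is met when either the investigator or the sponsor considers the relationship suspected. In practice this means adding the words *or the sponsor* after *investigator* in that sentence. The notice will then cover every serious, unexpected event that the sponsor treats as related under Section 8.3, and the existing IRB and consent steps will follow without further change.

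Leave the Section 8.3 trigger unchanged. Whether expedited reporting should also turn on either party's view is a matter of regulatory policy that these documents do not settle, and closing this gap does not depend on it.

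The cost is one phrase in a protocol amendment and at most a few additional notices. The SAP needs no change.
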